--	---

	 L A A B B C C D D E E F F G G H H H L	
2.6 Study Duration	
Estimate of 1 year required to recruit 50 patients (from an estimated 150 eligible) and another 6 months to complete the study analysis. A computer simulation indicates there should be 150 eligible subjects in 1 year. Of these, ~50 will be on prophylaxis and ~50 will decline participation and will be followed as no prophylaxis controls.
	
2.7 Statistical Analysis and Sample Size Justification	
The PI and local statistician will be responsible for analyzing the study data.
 
Variables/Time Points of Interest
 
The primary outcome variable is relapse of CDI within 8 weeks of study entry. Secondary outcomes are relapse of CDI within 4 weeks of study entry (the interval with highest protective antibody levels), all-cause mortality, time to relapse and duration of hospitalization.
 
Baseline variables collected for each subject include : age, gender, number/dates/treatment of prior CDI episodes, current PPI use and H2-blocker use, Charlson score, immunosuppression, Inflammatory Bowel Disease or Irritable Bowel Syndrome, use of cathartics/lactulose, and indication for current antibiotics.
 
Variables related to the past CDI episode include markers of disease severity : WBC, fever >100.5°F, creatinine, albumin – to generate a Zar score (Zar,2007)
 
Statistical Methods
 
The analysis population is the per-protocol population, with 2 major comparator groups – those receiving Bezlotoxumab and those with no prophylaxis. The latter will be comprised of 3 subgroups – the control group from the Wong study and 2 concurrent observation groups- a PASSIVE followup group of subjects undergoing chart review , and an ACTIVE followup group of subjects declining study drug but agreeing to phone followup at 8 weeks. All groups will be compared across baseline parameters cited above. Risk factors pre-specified for recurrent CDI include age, immunocompromise, and severe CDI will be compared across groups, and tested for associations for the major outcomes of CDI relapse and mortality at 4 weeks and 8 weeks.
 
In the Wong study, there was a remarkably equal distribution of variables among the
	

[figure not shown]

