antibiotic prophylaxis and no prophylaxis groups. We similarly expect no imbalance between our current study and observation groups in terms of risk factor distribution, though self-selection bias will be considered at the interim analysis after 30 intervention patients are enrolled.

Categorical variables will be compared using chi-square and Fisher's Exact analysis and continuous variables will be compared using Mann-Whitney analysis, with $p < 0.05$ considered to be significant.

In survival analysis (Kaplan-Meier), time to CDI relapse is defined from the date of bezlotoxumab study dosing or study refusal - to the date of relapse and limited by a maximum observable window of 8 weeks from the dose of bezlotoxumab. Subjects are censored on the date of death, if death occurred within the observable window, or at the beginning of a new potential antibiotic prophylaxis course (i.e.. If within the 8 week observation period there is receipt of metronidazole, oral vancomycin or fidaxomicin.) or receipt of fecal microbiota transplant. A Cox proportional hazards model will be used for group comparison when adjusting for covariates.

The survival analysis from the Wong study, demonstrating the benefits of antibiotic prophylaxis on preventing relapsed CDI, is summarized in the following figure:

Relapse Free Duration

For the second objective, rates of CDI relapse will be compared among study subjects with or without *C. difficile* colonization at study entry. This is an exploratory study to inform future studies. It is expected that 20% of subjects will be colonized at study entry (based on Sunkesula, 2013) –the expected number of these that relapse is unknown, as data is conflicting on whether colonization is protective or predictive of relapse.

Power/Sample Size:

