Estimates of group size and expected antibiotic prophylaxis outcomes are derived from the Wong and Van Hise studies which have similar or nearly identical design to the current proposal, albeit retrospective. In the Wong study, of 248 enrolled subjects, 104 received prophylaxis with metronidazole (n=63 total, 19 combined with vancomycin) or vancomycin (n=60), and 144 did not. In this latter group, 86 were \geq 60 yrs old of whom 23 relapsed, for a relapse rate of 26.7%. For the bezlotoxumab arm, the expected benefit is between a 43-54% reduction in relapse incidence (Gerdinger, 2018), with the variability based on the number of risk factors for CDI relapse in our population – all have at least 1 risk factor : most with age >65 and all with concurrent high-risk antibiotics. The expected CDI relapse rate in the active arm is therefore 12.2-15.2%. Thus

1. We need 62 bezlotoxumab subjects (at 12.2% relapse) to be 80% powered to detect a difference in outcomes vs. the no prophylaxis control population (with a relapse rate of 26.7%), with a two-tailed alpha=0.05.
2. We need 103 bezlotoxumab subjects (at 15.2% relapse) to be 80% powered to detect a difference in outcomes vs. the no prophylaxis control population (with a relapse rate of 26.7%), with a two-tailed alpha=0.05.

In 1 year, we expect 50 bezlotoxumab subjects and 50 no-prophylaxis controls in the prospective cohort. The numbers of subjects in the no-prophylaxis observational arms can be supplemented by retrospective chart reviews incorporating the same analysis used in the prospective study, or by merging with the control arm of the Wong study.

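### The stated 62 and 103 bezlotoxumab subjects fit a one-sample test against a fixed 26.7%; in the planned two-group comparison with 1:1 concurrent plus 86 historical controls, power is about 65% and 62%, not 80%

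*Combined protocol and SAP*

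**What the plan says.** Section 2.7, Power/Sample Size, makes two statements, both at two-tailed alpha 0.05 and against a 26.7% control relapse rate: "We need 62 bezlotoxumab subjects (at 12.2% relapse) to be 80% powered to detect a difference in outcomes vs. the no prophylaxis control population" and "We need 103 bezlotoxumab subjects (at 15.2% relapse) to be 80% powered to detect a difference in outcomes". No formula is given, and no number of controls is attached to either statement. The 26.7% comes from untreated patients aged 60 or over in the site's earlier retrospective study, 86 patients "of whom 23 relapsed, for a relapse rate of 26.7" percent.

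On the controls, the same section says "In 1 year, we expect 50 bezlotoxumab subjects and 50 no-prophylaxis controls in the prospective cohort", and adds that the control numbers "can be supplemented by retrospective chart reviews incorporating the same analysis used in the prospective study" or by merging with the retrospective study's control arm. Section 2.6 likewise expects about 50 patients who "will decline participation and will be followed as no prophylaxis controls". The Statistical Methods part of section 2.7 defines two comparator groups, bezlotoxumab and no prophylaxis. Of the no-prophylaxis group it says "The latter will be comprised of 3 subgroups": one historical and two concurrent. For the tests it says "Categorical variables will be compared using chi-square and Fisher's Exact analysis".

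The end of section 2.7 calls the study a pilot, plans an interim look at realistic timelines, and raises a 3 to 6 month extension to gain power. Section 2.9 gives 50 planned subjects.

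**The concern.** A calculation that counts only the bezlotoxumab arm treats the control rate as a known constant. The planned tests do not: they carry the sampling error of the controls as well. The 95% interval (Wilson) around 23/86 runs from about 18.5% to 36.9%, so the omitted error is not small.

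At stake is how the extension and a null result would be read. At 50 subjects a year, 3 to 6 more months brings the bezlotoxumab arm to about 62 to 75 (50 + 12.5 to 50 + 25). The lower end coincides with the stated target of 62, so at 12.2% a short extension would look sufficient for 80% power. The plan does not say in so many words that the extension will be judged against 62 or 103, but these are the only sample-size targets it offers for adequate power.

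**Working it through.** **Inputs** (all section 2.7): control rate p0 = 0.267; bezlotoxumab rate p1 = 0.122 or 0.152; two-sided alpha 0.05 (z = 1.96); power 80% (z = 0.8416); 86 historical controls; concurrent groups expected 50:50.

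**Step 1: reproduce the plan's figures.** One-sample test against a fixed p0:

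n = [1.96·√(p0(1−p0)) + 0.8416·√(p1(1−p1))]² / (p0−p1)²

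- At 12.2%: (0.8671 + 0.2755)² / 0.145² = 62.1
- At 15.2%: (0.8671 + 0.3022)² / 0.115² = 103.4

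These match 62 and 103. A two-sided, two-sample calculation at 1:1 gives 116 and 196 per arm, or 130 and 213 with continuity correction. One-sided at 1:1 it gives 92 and 154. None of these matches.

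**Step 2: two-group power at the stated numbers.** With n1 bezlotoxumab subjects, n2 controls and pooled rate p̄:

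power = Φ{ [(p0−p1) − 1.96·s0] / s1 }, where s0 = √[p̄(1−p̄)(1/n1+1/n2)] and s1 = √[p1(1−p1)/n1 + p0(1−p0)/n2]

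The plan gives no n2 for these scenarios. I take concurrent controls at 1:1 plus the 86 historical patients, pooled without adjustment.

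- 62 v 148 (62 + 86), 12.2%: p̄ = 0.2242, s0 = 0.0631, s1 = 0.0552; Φ(0.387) = 65.0%
- 103 v 189 (103 + 86), 15.2%: p̄ = 0.2264, s0 = 0.0513, s1 = 0.0478; Φ(0.304) = 61.9%

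Exact enumeration gives 65.5% and 62.8% for chi-square, and 62.5% and 59.8% for Fisher. With the observed 23/86 held fixed and only the concurrent controls random, exact chi-square gives 67.2% and 64.0%, and Fisher 64.0% and 61.0%.

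**Step 3: does another control size rescue 80%?** Normal approximation, all controls at 26.7%:

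| Controls | 62 at 12.2% | 103 at 15.2% |
|---|---|---|
| 1:1 concurrent only | 53.2% | 52.7% |
| 86 historical only | 58.1% | 49.7% |
| 50 concurrent + 86 | 64.1% | 57.2% |
| 1:1 concurrent + 86 | 65.0% | 61.9% |
| 1:1 concurrent + all 144 historical | 68.5% | 65.3% |
| 500 | 74.7% | 71.9% |
| 1000 | 77.2% | 75.7% |

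As n2 grows without limit the formula tends to the one-sample power, 79.9% and 79.8%. In this calculation, then, 80% is the limit reached only when control sampling error vanishes.

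**Step 4: the one-year and extended study.** Percentages without a label use the normal approximation; those with 23/86 fixed are exact chi-square.

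| Comparison | 12.2% | 15.2% |
|---|---|---|
| 50 v 50 | 45% | 29% |
| 50 v 136 | 56% (59% with 23/86 fixed) | 36% (37% fixed) |
| 75 v 161 | 73% (76% fixed) | 50% (50% fixed) |

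The one-sample method would give 88% and 64% at 75 subjects.

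**Step 5: bezlotoxumab subjects needed for 80%.**

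| Controls | 12.2% | 15.2% |
|---|---|---|
| As stated in the plan | 62 | 103 |
| n concurrent + 86 | 91 | 165 |
| n concurrent + 86, 23/86 fixed (exact chi-square) | 82 | 154 |
| n concurrent only | 116 | 196 |

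**The case against.** The strongest reply has four parts.

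- **No slip of arithmetic.** The one-sample formula returns the stated numbers, and the 26.7% benchmark is in plain view. That is so, but the figures are offered as the power of a comparison with the control population, and the planned comparison has two sampled groups. That the plan used a one-sample formula remains an inference; it is a strong one, since both numbers match from the plan's inputs alone.
- **The control sizes 148 and 189 are not in the documents.** This stands. They rest on extending the 50:50 expectation and adding the 86. The plan also names the historical control group without restricting it to those aged 60 or over, and permits chart-review controls of unstated number. The size of the shortfall therefore varies; its existence does not, because no control set in the working reaches 80%.
- **The effect is limited.** Also true. The study calls itself a pilot, plans 50 subjects and claims no 80% power for that number. At 15.2% even the extended study falls visibly short of the plan's own 103. The plan could be read as tying the extension to recruitment targets.
- **The control rate may exceed 26.7%.** The plan raises this, but the two statements are conditional on 26.7% and have to hold at that rate.

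**Conclusion.** The concern holds. Under the plan's own rates and alpha, 62 and 103 bezlotoxumab subjects give about 65% and 62% power in the planned comparison (67% and 64% with the historical result fixed). At 62 subjects and 12.2% relapse, the chance of a non-significant result is about 35% (33% with 23/86 fixed), not 20%. These figures assume that decliners accrue 1:1, that the 86 historical patients are pooled without adjustment, and that concurrent controls relapse at 26.7%. Across the control sizes examined, power at the stated numbers runs from about 50% to 77%.

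The error is confined to the two sample-size statements and, at 12.2%, to the extension sentence as far as it relies on the first of them. It should be fixed, but it does not undermine a 50-subject pilot.

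**What to change.** Change wording in section 2.7 only.

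- Replace the two statements with two-sample figures, and state the formula, the control size assumed and whether the historical result is treated as random or fixed. The sample sizes in the last table of the working can serve, each tied to its control assumption.
- If chart-review controls are to count towards power, state how many are assumed.
- State the power of the one-year comparison, at 50 v 50 and 50 v 136, for both relapse rates.
- In the extension sentence, replace the claim of reaching adequate power with the power that 62 to 75 subjects would give: about 65% to 73% at 12.2% with 1:1 plus 86 controls, and about 50% at 15.2% even at 75.

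No extra patients are asked for, and no test or endpoint changes. The cost is a protocol edit and a less favourable stated power.

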Given the prospective design, with more data available regarding relapse than in the Wong study (wherein outpatient records were not yet electronic) and the fact that relapse rates in the control group in the MODIFY studies were 39% in those over 65, its possible that more relapses will occur in the no-prophylaxis group than the 26.7% expected. This would lower the numbers needed to show a significant benefit. An interim analysis is planned after 6 months or 30 subjects enrolled, to re-assess realistic timelines for achieving significant results from this project. Notably, this is a pilot study which if it meets targets, could potentially be extended by 3 to 6 months to achieve statistically significant power. Alternatively, if study effects exceed expectations, a placebo-controlled design could be considered moving forward- for the pilot study, this is precluded by the larger sample size anticipated for such a project.

2.8 Specific Drug Supply Requirements	
The Bezlotoxumab drug supplies will be open label and provided by MSD.
 
The institution's research pharmacy will require bulk supplies from MSD (one large container of 10 courses at 1 time). As bulk supplies are provided by MSD, our institution's pharmacy will be responsible for preparing individual patient doses. A description as to how the clinical supplies are to be packaged and labeled for each patient will be added to the protocol.
 
Note: At conclusion of the study or upon drug expiration, the MSD GRS will be responsible for issuing a Drug Disposition Letter to the investigator for US based studies.
 
The investigator will be responsible for the destruction of the supplies at the study center pursuant to the ICH/GCP Guidelines, local regulations and the investigator's institutional policies. Clinical supplies will be received by a designated person (research pharmacist) at the study site, handled and stored safely and properly, and kept in a secured location to which only the investigator and designated assistants have access. Clinical supplies are dispensed in accordance with the protocol. The investigator is responsible for keeping accurate records of the clinical supplies, the amount dispensed to and returned by the patients, and the disposition at the end of the study.

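### The interim look and possible extension are not tied to pooled data and one final test, so testing relapse before and after extending could push the false-positive rate above 5%

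*Combined protocol and SAP*

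**What the plan says.** Three parts of Section 2.7 bear on this.

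- **Interim and extension (end of Power/Sample Size).** "An interim analysis is planned after 6 months or 30 subjects enrolled, to re-assess realistic timelines for achieving significant results from this project". The study, called a pilot, "could potentially be extended by 3 to 6 months to achieve statistically significant power", provided that it meets targets, a term the plan never defines. The next sentence adds that "if study effects exceed expectations, a placebo-controlled design could be considered" as a later step.
- **Interim, second mention (Statistical Methods).** Self-selection bias is to be considered "at the interim analysis after 30 intervention patients are enrolled". This trigger differs from the one above.
- **Error rate.** Statistical Methods names chi-square and Fisher's exact tests for categorical variables, with p below 0.05 "considered to be significant". The sample sizes are set "with a two-tailed alpha=0.05".

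The plan gives no alpha-spending rule, stopping boundary or adjusted threshold. It does not limit the interim to pooled data and does not commit to one final test. Section 2.8 says that the drug is open label, and Section 2.7 has the principal investigator and a local statistician analyse the data. The safety reviews in Section 2.9, after 12 and 25 subjects, are a separate matter.

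**The concern.** The interim is measured against reaching significance, not against accrual alone, and extension depends on undefined targets. The sentences just before the interim text note that a control relapse rate above 26.7% would reduce the number needed. Acting on that could mean looking at relapse by group.

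A test-then-extend path is also realistic. The plan says "We need 62 bezlotoxumab subjects (at 12.2% relapse) to be 80% powered to detect a difference in outcomes", and 103 at the smaller effect, but it expects only 50 treated subjects in the first year. A team with a non-significant result at 50 could extend and test again at 0.05 without breaching anything written. A significant result reached that way would not carry a 5% error rate, and the plan expects a major manuscript (Section 2.12). Once relapse by arm has been seen, the gap cannot be repaired.

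**Working it through.** **Inputs (Section 2.7).** Control relapse 26.7% (23/86); active-arm relapse 12.2% or 15.2%; two-sided alpha 0.05; power 80%; 50 treated and 50 concurrent controls in one year; interim at 30; extension of 3 to 6 months.

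**The plan's own figures.** A one-sample formula against a fixed control rate p0 reproduces them:

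n = [(1.96·√(p0·q0) + 0.842·√(p1·q1)) / (p0 − p1)]²

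- p1 = 0.122: [(0.867 + 0.275)/0.145]² = 62.1, stated as 62.
- p1 = 0.152: [(0.867 + 0.302)/0.115]² = 103.4, stated as 103.

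Both figures therefore assume one test at 0.05. They also treat 26.7% as known without error, which is a separate issue.

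**Size after extension.** Assume accrual stays at 50 a year. Three months adds 50 × 3/12 = 12.5, giving about 62. Six months adds 25, giving 75. Neither reaches 103.

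**Relapse tested between arms at every look.** Simulate relapse at 26.7% in both arms, test at each look, and count a false positive if any look has p < 0.05. The chi-square statistic is z = (a/n − b/m) / √[p̄(1 − p̄)(1/n + 1/m)], rejecting if |z| > 1.96. Here a and b are relapses among n treated and m controls, and p̄ is the pooled rate. Ranges are over separate runs of 200,000 or more trials.

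| Looks (treated subjects) | Chi-square, equal arms | Fisher, equal arms | Fisher, 86 historical controls |
|---|---|---|---|
| 50, 62 | 7.0–7.1% | 4.4–4.5% | 5.3–5.4% |
| 50, 75 | 7.7–7.8% | 5.0% | 5.8–5.9% |
| 30, 50 | 7.9–8.0% | 4.5–4.6% | 5.9% |
| 30, 50, 75 | 10.3–10.4% | 6.3–6.4% | 7.5–7.6% |

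Chi-square against the 86 historical controls gives about 6.8% to 9.4%. Fisher also inflates, but from a lower base: one Fisher test at 50 per arm rejects about 3.1% of the time under no effect.

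**Extension decided on unblinded data at 30, one final test only** (normal approximation).

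- Extend on a favourable trend (z above 0, 0.5 or 1.0): 4.3% to 5.0%.
- Choose the final size to maximise the chance of rejection: 5.9% if the maximum is 75, 6.5% if it is 103.

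**Extension decided on enrolment or pooled relapse, one final test.** 5.0%.

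**Trigger.** At 50 treated and 50 declining a year, 30 subjects of both kinds means about 15 treated, against 30 treated under the other wording. This inconsistency does not itself change the error rate.

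**The case against.** A reader might infer that an interim efficacy test is planned. The documents do not support that. The two stated purposes are reassessing timelines and considering self-selection bias, and the second is a check of baseline comparability. The p < 0.05 sentence is a general methods line that says nothing about repeated testing. This stands, so the point must be conditional.

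A reader might also take the sentence about effects exceeding expectations as a rule for adapting this study. It concerns a later placebo-controlled design, which the plan says is precluded for the pilot. It is not evidence of repeated testing here.

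The extension can also be read as closing a shortfall known in advance: 50 expected, 62 needed, and three more months reach about 62. The targets may simply be enrolment. That is a fair reading, and on it alpha stays at 5%. But the text does not secure it, because the targets are undefined and no data source for the decision is named.

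The choice of test matters too. The plan does not say whether chi-square or Fisher applies to the primary endpoint. With Fisher and equal arms, every two-look path stays at about 5% or below.

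Finally, in a non-randomised, open-label pilot whose controls are decliners or historical patients, confounding and the open choice of control group may bias the result more than repeated looks. That lowers the priority of the point but does not remove it: the plan still sets 80% power and a significance threshold, and the gap costs almost nothing to close.

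**Conclusion.** The concern holds in conditional form. The plan permits a between-arm look and a test both before and after an extension, with no adjustment, but it does not state that either will happen. The claim that the false-positive rate will exceed 5% is not supported; the claim that it can is.

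The size depends on the route taken:

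- about 7% to 10% with repeated chi-square tests;
- about 4.5% to 6.4% with repeated Fisher tests and equal arms, or 5.4% to 7.6% against 86 historical controls;
- about 4.3% to 6.5% if unblinded data drive the extension but only one final test is made;
- 5% if only enrolment or pooled data drive it.

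These figures assume 26.7% relapse in both groups, looks at the sizes shown, and, for 62 and 75, accrual continuing at 50 a year. The 6.5% upper end needs a final size of 103, beyond what a 3 to 6 month extension would reach at that rate. The change should be made, but it ranks below the confounding and control-group problems.

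**What to change.** In Section 2.7:

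1. State that the interim uses only enrolment, consent rate, completeness of follow-up, baseline comparability (which keeps the self-selection check) and the relapse rate pooled over arms, with no between-arm comparison of relapse. Relapse in the control group alone should not be shown beside the pooled rate, because the treated rate could then be worked out.
2. Define the targets in those terms.
3. Decide on extension and fix the final number before any between-arm test.
4. Name the primary test, chi-square or Fisher, and run it once at two-sided 0.05.
5. Use one interim trigger in both places, and say whether the 30 counts treated subjects only.

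Only if a between-arm look is wanted, prespecify alpha spending over all looks, including any after the extension.

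**Cost.** Items 1 to 5 are wording only. They leave alpha and the stated sample sizes unchanged, and the team gives up an early between-arm result. Alpha spending instead means a stricter final threshold. As an illustration, constant boundaries need p < 0.032 for looks at 50 and 75, or p < 0.023 for looks at 30, 50 and 75. In the plan's own formula that means about 72 to 79 treated subjects in place of 62, and 119 to 130 in place of 103. An O'Brien-Fleming-type rule would keep the final threshold closer to 0.05.

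### The 62 and 103 treat the 26.7% control rate as exact; with the planned two-group tests, a 3 to 6 month extension does not give 80% power with the expected controls

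*Combined protocol and SAP*

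**What the plan says.** Section 2.7, Variables/Time Points of Interest: "The primary outcome variable is relapse of CDI within 8 weeks of study entry".

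Section 2.7, Power/Sample Size, takes the control rate from the historical no-prophylaxis patients aged 60 or over, 86 in number, "of whom 23 relapsed, for a relapse rate of 26.7" percent. It expects a 43-54% reduction, hence 12.2-15.2% relapse on bezlotoxumab, and draws two requirements at two-sided 5%: "We need 62 bezlotoxumab subjects (at 12.2% relapse) to be 80% powered" and "We need 103 bezlotoxumab subjects (at 15.2% relapse) to be 80% powered".

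On accrual, section 2.6 gives "Estimate of 1 year required to recruit 50 patients", and section 2.7 gives "In 1 year, we expect 50 bezlotoxumab subjects and 50 no-prophylaxis controls in the prospective cohort". Control numbers "can be supplemented by retrospective chart reviews incorporating the same analysis used in the prospective study", or by merging with the historical control arm. No upper limit is set.

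The extension sentence in the same section reads "if it meets targets, could potentially be extended by 3 to 6 months to achieve statistically significant power". Just before it, the plan notes that control relapse could exceed 26.7%, citing 39% in patients over 65 in the earlier bezlotoxumab trials, and that this would reduce the numbers required.

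Section 2.7, Statistical Methods, compares categorical outcomes between groups by chi-square and Fisher's exact tests. The primary population is per-protocol.

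**The concern.** There are two separate problems. First, the sample-size formula does not match the analysis. A rate estimated from 86 patients has its own sampling error, and the concurrent controls add theirs. A test that compares two groups must carry both errors, whereas the figures of 62 and 103 carry neither.

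Second, the length of the extension does not match the range of requirements. Three to six months at the stated accrual reaches the lower requirement and stops well short of the upper one.

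A sponsor, ethics board or later reader could take the extended study to be adequately powered over the stated effect range. With the controls the plan expects, it would more likely than not miss significance at the 43% reduction, even if the drug works as assumed.

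**Working it through.** **Inputs.** Control rate p0 = 0.267 (23/86), bezlotoxumab rate p1 = 0.122 or 0.152, two-sided alpha 0.05 (z = 1.960), power 80% (z = 0.842), all from section 2.7. Accrual is 50 bezlotoxumab patients and 50 concurrent controls per year (sections 2.6 and 2.7).

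**1. Reproducing 62 and 103.** One-sample formula: n = [1.960·√(p0(1−p0)) + 0.842·√(p1(1−p1))]² / (p0−p1)².
- p1 = 0.122: (0.8671 + 0.2755)² / 0.145² = 62.1
- p1 = 0.152: (0.8671 + 0.3022)² / 0.115² = 103.4

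Both stated figures are recovered. None of the two-group variants tried recovers them: one-sided gives 92 / 154, continuity-corrected 130 / 213, arcsine about 113 / 193, and five controls per bezlotoxumab patient 74 / 123.

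**2. Size for the planned comparison.** Two equal groups, with p̄ = (p0+p1)/2: n per group = [1.960·√(2p̄(1−p̄)) + 0.842·√(p1(1−p1) + p0(1−p0))]² / (p0−p1)².
- p1 = 0.122: (1.0971 + 0.4631)² / 0.145² = 115.8, so 116
- p1 = 0.152: (1.1280 + 0.4795)² / 0.115² = 195.4, so 196

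These are for uncorrected chi-square. Under Fisher's exact test, the same sizes give 76.5% and about 77% power, so that test needs more.

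**3. What the extension yields.** Accrual is 50/12 = 4.17 per month.
- 15 months: 62.5 patients
- 18 months: 75 patients
- 103 patients: 103/4.17 = 24.7 months, or 12.7 months beyond year 1

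**4. Power at those sizes.** Control rate 26.7%, full enumeration of both binomials. Each cell shows 12.2% / 15.2% relapse. The larger control figure adds the 86 historical patients to 1:1 concurrent controls.

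| Bezlotoxumab | Controls | Chi-square, uncorrected | Fisher's exact |
|---|---|---|---|
| 50 | 50 | 46.3% / 29.7% | 36.0% / 21.9% |
| 50 | 136 | 57.5% / 37.1% | 54.9% / 34.2% |
| 62 | 62 | 53.0% / 34.3% | 44.9% / 27.3% |
| 62 | 148 | 65.5% / 43.4% | 62.5% / 39.9% |
| 75 | 75 | 62.5% / 41.2% | 54.0% / 33.6% |
| 75 | 161 | 73.5% / 50.1% | 69.9% / 46.0% |
| 75 | 300 | 79.8% / 56.2% | 77.9% / 53.7% |
| 75 | 400 | 82.0% / 58.5% | 80.4% / 56.1% |

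**5. The ceiling.** With unlimited controls the comparison becomes the one-sample test. Its power at 75 is Φ[(|p0−p1|·√75 − 1.960·√(p0(1−p0))) / √(p1(1−p1))] = 88% at 12.2% and 64% at 15.2%. Enumeration with 20,000 controls gives 87.9% and 65.0%.

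**6. A control rate of 39%.** With 75 per group, chi-square power is 82% for a 54% reduction (17.9% relapse) and 61% for a 43% reduction (22.2% relapse). With 161 controls, all at 39%, it is 92% and 74%.

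**The case against.** The strongest defence is that the plan is open about its limits. It calls itself a pilot, shows 50 expected against 62 to 103 needed, words the extension as a possibility, and schedules an interim to revisit timelines. It also leaves the number of chart-review controls open and warns that control relapse may be higher.

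Much of this stands. A reader might infer that the extension misses the plan's own requirement altogether. It does not, because three months reaches 62. On the plan's one-sample formula, 75 suffices if bezlotoxumab relapse is about 13.3% or lower (a reduction of about 50%). For a 43% reduction it suffices if the control rate is about 33.9% or higher; at 39%, that formula needs about 61.

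A reader might also infer that power is below 80% whatever the controls. That is wrong at 12.2%, where 300 to 400 controls are enough by chi-square.

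It is also tempting to fault the interim as too small to tell 12.2% from 15.2%, or as lacking a by-group boundary. The documents give it neither task. It is there to reassess timelines and to consider self-selection. The undefined targets qualify the extension, not the interim, and are a missing detail.

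What the defence does not answer is the formula. The pilot label and the hedged wording do not make a one-sample calculation fit a two-group test. The 43% reduction also stays below 80% at 75 bezlotoxumab patients: at a 26.7% control rate with any number of controls, and at 39% with 75 or 161.

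**Conclusion.** The concern holds in a limited form. The figures 62 and 103 give 80% power only if 26.7% is known without error; the planned comparison needs about 116 or 196 per group. The longest stated extension gives about 75 bezlotoxumab patients. With the controls the plan expects, chi-square power is then about 62-73% at the favourable end of the effect range and 41-50% at the other, and lower under Fisher's exact test. More controls can repair the favourable end but not the other. A higher control rate helps only in part.

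This rests on constant accrual at 50 per year, all control groups relapsing at the same rate (26.7% unless stated), and no losses. Section 2.3 removes patients who receive qualifying prophylaxis from the primary analysis, so evaluable numbers could be smaller and power lower.

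It should be corrected, but it does not make the pilot unworkable.

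**What to change.** In section 2.7, Power/Sample Size, replace the 62 and 103 statements and the power aim of the extension with the two-group power expected at 50, 62 and 75 evaluable (per-protocol) bezlotoxumab patients. State the number of controls planned at each size, and compute power for one named final test. The table above can serve once that test is chosen, since Statistical Methods now names both chi-square and Fisher's exact.

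Describe the result as a pilot estimate and report the relapse difference with its 95% confidence interval. As a guide to precision, with 75 per group and 12.2% against 26.7%, the half-width is 1.96·√(0.122·0.878/75 + 0.267·0.733/75) = 12.5 percentage points around a difference of 14.5.

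As a minor wording point, use one interim trigger. Statistical Methods says 30 intervention patients; Power/Sample Size says six months or 30 subjects. At planned accrual, six months gives 25 bezlotoxumab patients, and 30 are reached at 7.2 months.

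The change costs a paragraph or two of text and no patients. The real price is that the plan gives up the claim of a powered comparison.
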